1. STUDY OBJECTIVES

1.1 Primary Objective

We will assess the effects of the proposed study interventions on mood, urinary melatonin, sleep and activity to test the following specific hypothesis:

For PMDD patients in the symptomatic luteal phase, LWT+AM BWL, compared

with EWT+PM BWL, will: A) Improve mood on rating scales; B) Phase-advance urinary melatonin timing measures in relation to clock time and sleep measures; C) The magnitude of the mood change will correlate with the magnitude of the phase-advance in melatonin.

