9. STATISTICAL CONSIDERATIONS

9.1 General Design Issues

The design is a randomized cross-over contrasting LWT+AM bright light vs. EWT+PM bright light administered in the luteal phase of two separate menstrual cycles, and preceded by 2 evaluation months. To lessen the patient's burden, the 1-night EWT or LWT and the following 7-day BWL interventions will be conducted at home, given at a fixed point in each menstrual cycle, from day 1 to 7 after the mid-cycle LH surge. We anticipate that LWT+7 days of AM BWL (vs. EWT+PM BWL) will produce much greater mood benefits and larger physiological responses, than the one-time light pulses used in our earlier phase-shift studies.

The wake therapy and light interventions proposed in this application are based on our previous studies in PMDD and key published experiments by other investigators that indicate that the combined interventions are efficacious in other mood disorders after one week of treatment and maintained at 9-months follow-up. To provide optimal timing of interventions, we will administer wake therapy in the early-night vs. late-night and light pulses in the AM vs. PM at selected times in relation to sleep (within 30 min of waking and 90 min before sleep onset, respectively).

A crossover treatment design is employed to compare LWT+AM BWL vs. EWT+PM BWL responses within the same individual. As wake interventions lose effectiveness after 1 day, and light treatment effects after 3-4 days, we anticipate minimal carry-over effects of the wake plus light interventions administered a month apart. To further ensure no carry-over effects, there will be a month of no-intervention between the 1st and 2nd treatments. Because our previous studies clearly indicated differences between PMDD and NC subjects occurred primarily in the luteal menstrual cycle phase, we will treat during this menstrual cycle phase rather than in the follicular phase.

Hypothesis (H) 1: For PMDD patients in the luteal phase, LWT+AM BWL, compared with EWT+PM BWL, will A) Decrease scores on SIGH-SAD, BDI, BAI, and DMR, and increase global assessment of treatment effectiveness from baseline to post-intervention; B) Phase-advance urinary melatonin timing measures (acrophase, onset and offset time) in relation to clock time and to sleep measures (onset, end time and mid-sleep times); C) The magnitude of the phase-advance (B, above) will correlate with the magnitude of the symptom changes (A, above) by linear regression.

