9.5 Outcomes

9.5.1 Primary Outcome

- Treatment-Related Mood Rating Changes from Baseline (month 2) to post intervention (months 3,5) :
Mood ratings include Hamilton Rating Scale for Depression (HRSD), Beck Depression Inventory (BDI), atypical depression symptoms as part of the Structured Interview Guide for the Hamilton Depression Rating Scale, Seasonal Affective Disorders version (SIGH-SAD), Beck Anxiety Inventory (BAI), mania ratings, the Psychological General Well-Being Index (PGWI) and daily mood self-ratings (DMR) that include core PMDD symptoms of anxiety and irritability as required during diagnostic evaluation, before, during and after each wake and light intervention at the same time of day (between 15:00-17:00 h). To assess more acute effects on mood that may occur more rapidly during the wake interventions, subjects will complete DMRs twice daily beginning the evening before the wake therapy intervention and continuing until the morning after the recovery night of sleep.
- Treatment-Related Urinary 6-sulfatoxymelatonin (6-SMT) Changes from Baseline (month 2) to post intervention (months 3,5) :
6-SMT is a principal melatonin metabolite that is abundant in urine, well correlated with plasma melatonin, and serves as an excellent marker for circadian phase response.
- Treatment-related changes in objective and subjective sleep measures:
Using actigraphy, we will obtain objective measures of the sleep/wake cycle to ensure appropriate sleep/wake times during wake therapy, and during the light interventions as it is an important biological rhythm with which to compare the intervention-induced melatonin rhythm changes. To assess subjective sleep quality, we will use the Pittsburgh Sleep Quality Index (PSQI) and a visual analogue scale.

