Specifically, data for hypothesis 1.A. will be analyzed using a Random Regression Model (RRM), a generalized linear model described by Gibbons et al.,⁷⁴ Hedeker et al.⁶⁹ and Laird.⁷⁵ The random effects method has several advantages over more traditional analytic approaches such as a change score, end-point or repeated measures analysis of variance. This method allows the inclusion of subjects with missing data or those who were terminated early in the study, without relying on data imputation procedures. This method provides an estimate of the individual variability around the population trend, the variability of the individual intercepts (baseline values) and slopes (changes across time), and the correlation between them. A fully saturated treatment by time model will be utilized for inference. Co-variance structure will be chosen based on Akaike's Information Criterion (AIC). Random treatment effects also will be evaluated for importance based on the model AIC. This plan allows for any group level effects to be incorporated into the model. Denominator degrees of freedom will be calculated using the Kenward-Roger small sample correction. All subjects will be included in the analyses, and we will not focus only on subjects who complete the study. Our methods for data analyses include all subjects with any valid data points in the analyses. Secondary analyses will be performed on data from completers. Type 1 error will be controlled by correcting the p-value per domain. For hypothesis 1.B, an individual's slope for each of the dependent variables listed above will be calculated and will be used for correlational analysis using the Pearson method. In addition, we will examine the number of responders. The operational definition of the criteria for

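### Section 9.6 gives hypothesis 1.B, the morning-versus-evening difference in melatonin timing, only a Pearson correlation; no treatment contrast is specified for this primary outcome

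*Combined protocol and SAP*

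**What the plan says.** Section 1.1 and Section 9.1 both state Hypothesis 1 as a comparison of the two treatments. In Section 9.1 part B reads "B) Phase-advance urinary melatonin timing measures (acrophase, onset and offset time) in relation to clock time and to sleep measures". Part C is the separate association claim: "The magnitude of the phase-advance (B, above) will correlate with the magnitude of the symptom changes (A, above) by linear regression". Section 9.5.1 lists the change in 6-SMT from Month 2 to Months 3 and 5 under the primary outcome.

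Section 9.6 assigns methods by hypothesis letter:

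- **1.A:** "data for hypothesis 1.A. will be analyzed using a Random Regression Model (RRM"). The same paragraph adds "A fully saturated treatment by time model will be utilized for inference".
- **1.B:** each individual's "slope for each of the dependent variables listed above will be calculated and will be used for correlational analysis using the Pearson method".
- **1.C:** to be handled in the same way as 1.B.
- **Multiplicity:** "Type 1 error will be controlled by correcting the p-value per domain".

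Section 9.6 then assigns analyses to hypotheses 2.A, 2.B, 3.A and 3.B, which the supplied text does not state.

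**The concern.** 1.B is a claim about a mean difference: melatonin timing should be earlier after the morning treatment than after the evening one. A Pearson coefficient describes how two variables move together across women. It gives no difference in hours, no confidence interval for one, and no valid test of whether one exists.

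Two errors become possible. A significant correlation could be reported in support of 1.B when the treatments do not differ in phase. A real phase difference could go untested, or be tested with a model chosen after the data are seen. The trial's aim is to show that timed treatment works by correcting melatonin and sleep phase, so this contrast carries the mechanistic claim.

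**Working it through.** **1. Is the contrast specified anywhere else?** These are the other places that could supply it.

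| Place | What it offers | Treatment contrast for 6-SMT? |
|---|---|---|
| Section 3 | Intent to assess phase changes and phase-shift responses | No method given |
| Section 6.2.6 | Reasons for choosing the random regression model; not limited to mood | No outcome or contrast named |
| Section 9.2 | Power for the primary hypotheses, in the plural, under that model | Power statement only; 6-SMT not named |
| Section 9.6, 6-SMT processing | Derives acrophase, amplitude, mesor, onset and offset | Stops at derivation |
| Section 9.6, Actiwatches | Compares activity, sleep and light exposure | Not 6-SMT |
| Section 9.6, later text | Examines outcomes according to the melatonin-sleep phase angle | Phase is explanatory, not the outcome |

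None gives a model, test or estimand. The documents also give no effect size, SD or power for 6-SMT, so there is no plan figure for 1.B to reproduce.

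**2. What would a contrast deliver?** Inputs borrowed from Section 9.2, none specific to melatonin: difference 0.5 SD, correlation ρ = .45, alpha .05 (two-sided). The analysis is a paired t test on complete pairs.

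- SD of the difference = √(2(1 − ρ)) = √1.10 = 1.049
- Standardised difference = 0.5 / 1.049 = 0.477
- Noncentrality at n = 40: 0.477 × √40 = 3.02, which gives power .836 from the noncentral t distribution

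| n | ρ = 0 | ρ = .2 | ρ = .45 | ρ = .7 |
|---|---|---|---|---|
| 40 | .587 | .684 | .836 | .978 |
| 36 (40 × .90) | .541 | .635 | .794 | .964 |
| 34 (40 × .85) | .517 | .609 | .770 | .955 |

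The ρ = .2 column is there because two autoregressive steps at .45 give .45² = .20. The smaller n apply Section 9.2's 10% and 15% drop-out to 40. If the per-domain correction were Bonferroni over three timing measures (an assumption, alpha .05/3 = .0167), power at ρ = .45 would be .695 at n = 40 and .604 at n = 34.

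**3. What does the Pearson test respond to?** Its coefficient is computed after subtracting the means. Moving every value in one arm by a constant therefore leaves it unchanged, and the same holds for within-woman differences. It does change if both arms are pooled, because the arm shifts then add covariance. With shifts of 1 SD in both variables, the induced correlation is (1 × 1/4) / (1 + 1/4) = .20.

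Simulation: 20,000 runs per row, n = 40, unit-SD changes in melatonin and mood, within-woman correlation .45 for each, individual melatonin-mood link r. Entries are rejection rates.

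| r | Melatonin shift (SD) | Mood shift (SD) | Pearson, one arm | Pearson, differences | Pearson, pooled | Paired contrast |
|---|---|---|---|---|---|---|
| 0 | 0 | 0 | .050 | .054 | .073 | .050 |
| 0 | .5 | 0 | .050 | .051 | .071 | .833 |
| 0 | .5 | .5 | .052 | .051 | .101 | .831 |
| 0 | 1 | 1 | .049 | .050 | .453 | 1.000 |
| .3 | 0 | 0 | .476 | .484 | .758 | .051 |
| .3 | .5 | 0 | .476 | .487 | .742 | .838 |

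One-arm and difference versions follow the link and ignore the treatment shift. The pooled version responds to some shifts, but it mixes them with the link and ignores that each woman contributes twice, so it rejects about 7% when nothing is present. None of the three tests 1.B.

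**The case against.** The best reply is that this is a labelling slip. Section 9.1 puts the correlation under 1.C, and Section 9.6 refers to hypotheses the text does not state, so its lettering is unreliable. There are also signs that a model for 6-SMT was intended: Section 9.6 describes individual slopes as a product of the random regression model, Section 9.2 ties that model to more than one primary hypothesis, and a per-domain correction implies inference beyond mood. All this is plausible evidence of intent. It does not supply a contrast: read literally, 1.B has an invalid test; read as a slip, it has none.

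Three criticisms of the figures have force.

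- Section 9.6 does not say what the slopes are correlated with. Melatonin against mood, the three ways of pairing, and the link of .3 are assumptions.
- The Précis recruits 48 women to obtain 40 completers, so subtracting drop-out from 40 may count it twice. On that reading n = 40 applies. However, Section 10.3.3 keeps in the study women who cannot collect urine, so fewer than 40 may have 6-SMT data.
- The power of a paired contrast does not measure the harm of leaving the contrast unwritten. It shows only what a suitable analysis could detect.

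It is also fair that 1.C is stated separately, so a careful reader could see which hypothesis a correlation supports. Section 9.6 nevertheless assigns the correlation to 1.B.

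**Conclusion.** The concern holds. A listed primary outcome has a directional treatment hypothesis and no valid prespecified treatment comparison, so the text must be corrected before analysis. This rests on the wording alone and does not depend on the simulation.

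The size is illustrative. Under the borrowed 0.5 SD and correlation .45, a paired contrast with 40 complete pairs has 84% power (59% to 98% for correlations from 0 to .7), before any multiplicity correction. If the Pearson test is melatonin against mood change, within one arm or on differences, its rejection rate is unrelated to the treatment shift: about 5% with no individual link, and about 48% with a link of .3 even when the treatments do not differ in phase.

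**What to change.** In Section 9.6:

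1. Assign 1.B a within-woman crossover mixed model for each 6-SMT timing measure (acrophase, onset, offset) and for its phase angle to sleep. Use treatment and period as fixed effects, woman as a random effect, and all available periods. The Month 2 baseline may be included, but a single value per woman cancels in complete pairs.
2. Report the morning-minus-evening difference in hours with its confidence interval, under the per-domain correction already stated.
3. Move the correlation sentence to 1.C and reconcile Pearson there with the linear regression named in Section 9.1. State how the two values per woman enter, so that the treatment effect is separated from the individual association.
4. Correct or delete the references to hypotheses 2 and 3.

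The cost is SAP wording only. The urine collections in Months 2, 3 and 5 are already in the plan, and no procedure or visit changes.

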2.2 Study Rationale

Interventions: The wake therapy and light interventions proposed in this application are based on our previous studies in PMDD³⁶⁻³⁹ and key published experiments by other investigators that indicate that the combined interventions are efficacious in other mood disorders after one week of treatment and maintained at 9-months follow-up.¹⁷⁻³¹ To provide optimal timing of interventions, we will administer wake therapy in the early-night vs. late-night and light pulses in the AM vs. PM at selected times in relation to sleep (within 30 min of waking and 90 min before sleep onset, respectively). These times were selected to examine phase-advance and phase-delay responses without disrupting sleep. Successful light treatment is associated with a phase-shift of the melatonin rhythm as noted by Epperson et al.⁴⁰ in a randomized trial of bright light therapy for antepartum depression and by Terman et al.⁴¹ in winter depression. In this proposal focusing on mood effects, we will administer 7 days of AM or PM light after wake and before sleep, respectively, for 60 min using a light-emitting diode (LED) device. The advantage of LEDs over conventional light boxes (fluorescent or incandescent) is that LEDs can be selected to emit light with energy concentrated at wavelengths of 450-480nm to which the human circadian system is most sensitive.⁴²⁻⁴⁴ Thus LEDs are not only more efficient, but smaller and light-weight, further enhancing patient compliance. Clinical effects on mood generally occur within 3-4 days after the onset of treatment, and expire within 3-4 days after discontinuation of treatment.^{45, 46}

A crossover treatment design will be employed to compare LWT+AM BWL vs. EWT+PM BWL responses within the same individual. As wake interventions lose effectiveness after 1 day, and light treatment effects after 3-4 days, we anticipate minimal carry-over effects of the wake plus light interventions administered a month

apart. To further ensure no carry-over effects, there will be a month of no-intervention between the 1st and 2nd treatments. Because our previous studies clearly indicated differences between PMDD and NC subjects occurred primarily in the luteal menstrual cycle phase, we will treat during this menstrual cycle phase rather than in the follicular phase.

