3. STUDY DESIGN

Forty PMDD subjects will be recruited. Menstrual cycle phase will be established by measuring the mid-cycle LH surge using a urinary colorimetric assay (Clearblue® colorimetric LH assay, Princeton, New Jersey). Failure to ovulate will exclude the subject from participating that month, and the study will be postponed until a following month when ovulation can be documented.

Overall Design (see Figure 1): Month 1 consists of a screening evaluation using daily mood ratings (DMR) (see Section 6: Subject Selection). In Month 2, evaluations are continued, the Structured Clinical Interview for DSM-IV (SCID)^{51, 52} and documentation of ovulation by the LH surge (approximately menstrual cycle day 14) are performed. In the Month 2 luteal phase, PMDD subjects will collect overnight urine samples for 6-SMT and reproductive hormones (RH) (estradiol, progesterone, FSH, LH, prolactin) starting 8-9 days after the LH surge (approximately menstrual cycle days 22-23). These baseline urine sample collections are timed to coincide with post-intervention measures in months 3 and 5. Starting in Month 3, after the LH surge (luteal phase), subjects will undergo a night of LWT (sleep 21:00-01:00 h, followed by wake) vs. EWT (wake until 03:00 h followed by sleep until 07:00 h) at home. We selected the specific wake and sleep times based on our previous work in

PMDD.^{36, 37} The following day, subjects will receive the light intervention for 7 consecutive days: days 1-7 after the LH surge (approximately menstrual cycle days 15-21). We will randomize subjects to 60 min of either AM bright white light (LED of 1350 lux at 20 inches) starting within 30 minutes of their habitual wake time, or PM bright white light ending 30 min before their habitual sleep onset time. After completing seven days of light exposure, subjects again will collect 30+ hours of urine samples over 2 nights (between days 8-9 after the LH surge, approximately menstrual cycle day 22-23). The following Month 4 (Washout) will be a month of no intervention to prevent any carry-over effects from the Month 3 intervention affecting measures in Month 5. Mirroring Month 3 timing, in the luteal phase of Month 5, subjects will receive the alternate wake therapy (LWT or EWT) and light exposure (AM or PM), followed by 2 overnight collections of urinary 6-SMT and RH samples. See Fig. 1, below.

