This design allows us to complete the studies at least two days before the next expected menstrual period. Measuring the circadian profile of urinary melatonin over 2 nights for 30+ h will allow us to assess phase, duration and amplitude changes of melatonin reflective of the underlying circadian pacemaker. In addition, we will assess phase-shift responses of melatonin to light in relation to other critical biological rhythm measures of sleep and activity. To document the sleep/wake cycle and exposure to light intensity and spectra, we will use the Actiwatch device (see description below).

[figure not shown]

Figure 1. Study flow: The luteinizing hormone surge (LHS) documents ovulation, c. menstrual cycle day (CD) 14. Urine samples for 6-sulphatoxy-melatonin (6-SMT) and reproductive hormones (RHs) will be collected for 30+ hours over 2 nights between days 8-9 after the LH surge (c. CD 22-23) in months 2,3,5; actigraphy will begin the day of LHS and continue until day 10 after the LHS (CD 14-24) of months 2,3,5; late wake therapy (LWT) or early wake therapy (EWT) will be administered at home on the night of the LHS; bright morning (AM) or evening (PM) light will be administered on days 1-7 after the LHS (CD 15-21) in a counterbalanced, cross-over design in months 3 and 5. Mood ratings (HRSD+BDI) will be collected as follows: Months 1 & 2 – once per week; Months 3 & 5 – LHS + 0 (Pre-

LWT/EWT), daily LHS +1 → LHS + 2 and once the evening after last treatment (LHS +7/8). Visual Analogue Scales (VAS) for depressed mood, anxiety, affective lability, irritability (Daily Mood Ratings)(core PMDD symptoms) collected daily during Months 1 & 2, and twice daily on LHS + 0 through LHS + 2 (for wake therapy effects) and daily LHS + 3 through LH + 10 (for light treatment effects) in Months 3 & 5. HRSD will be collected once during Month 4 and a once a month after Intervention 2 to monitor relapse.

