response on the mood measures, the HRSD, SIGH-SAD and the BDI, is a decrease of > 50% in the pre-treatment/baseline score, while the remission criterion will be a decline to a value < 8 on the SIGH-SAD and BDI as per Terman et al.⁴¹ We will compare percentages of PMDD subjects achieving the Terman criteria in groups receiving different interventions using Chi Square analysis. Results from Expectation Forms and Horne-Ostberg Scales will be examined in relation to the magnitude of mood change after interventions as assessed by mood ratings, the Psychological General Well-Being Index (PGWI), and side effects checklists. We also will examine the effect of diagnosis and light intervention on measures of subjective sleep quality as measured by the Pittsburgh Sleep Quality Index (PSQI), and differences between groups or intervention on outcome measures as a function of the phase-angle difference (PAD) between melatonin timing (acrophase, onset, offset) and sleep (onset, end-time, mid-sleep) measures. Data for hypothesis 1.C will be analyzed similar to hypothesis 1.B. Data for hypothesis 2.A will be analyzed similar to hypothesis 1.A using RRM. Data from LWT + AM BWL, however, will be used only. Data for hypothesis 2.B will be analyzed similar to hypothesis 1.B by using individual slope in the correlational analysis. Data for hypothesis 3.A will be analyzed similar to hypothesis 1.B, and for hypothesis 3.B, similar to hypothesis 1.A using only EWT +PM BWL treatment data.

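### The H1.C correlation of mood change with melatonin phase shift uses an undefined slope with no treatment or sequence term; two natural readings inflate its type I error

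*Combined protocol and SAP*

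**What the plan says.** Section 9.1 states the hypothesis: "The magnitude of the phase-advance (B, above) will correlate with the magnitude of the symptom changes (A, above) by linear regression". Section 9.6 gives the analysis in two steps. For H1.B, an individual's "slope for each of the dependent variables listed above will be calculated and will be used for correlational analysis using the Pearson method". Then: "Data for hypothesis 1.C will be analyzed similar to hypothesis 1.B".

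The only description of a slope is in Section 9.6, in the account of the random regression model for H1.A: "slopes (changes across time". For the correlation, the plan does not say whether the slope runs over all months, is taken separately by treatment, or is a between-treatment difference. No treatment, period or sequence term is named. Section 9.6 restricts H2.A and H3.B to one treatment's data; it states no such restriction for H1.C.

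On the data, the Figure 1 legend in Section 3 says urine "will be collected for 30+ hours over 2 nights between days 8-9 after the LH surge (c. CD 22-23) in months 2,3,5". Section 9.5.1 makes Month 2 the common baseline: "Treatment-Related Urinary 6-sulfatoxymelatonin (6-SMT) Changes from Baseline (month 2) to post intervention (months 3,5". In Month 5, "subjects will receive the alternate wake therapy (LWT or EWT) and light exposure (AM or PM), followed by 2 overnight collections". Section 2.2 says of the intervention times: "These times were selected to examine phase-advance and phase-delay responses without disrupting sleep".

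**The concern.** Each treatment month has one 6-SMT collection, made after treatment. Within one treatment, the most that exists is a two-point change from Month 2. A single slope per woman over Months 2, 3 and 5 passes through both treatments, so its sign can depend on which treatment came first. The mood slope depends on order in the same way. Two measures that both follow the randomised sequence will correlate across women even when no woman's mood response has anything to do with her phase response.

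Pooling two changes per woman has the same weakness by treatment instead of by sequence. It also counts 80 rows as independent when each pair shares a baseline.

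H1.C is part of the primary objective (Section 1.1) and carries the mechanistic claim in the Précis that treatment improves mood by correcting phase. Participants are not blind (Section 6.2.3). Expectation could move mood by treatment while light timing moves phase, and an unadjusted correlation could report the two as linked.

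**Working it through.** The plan gives no sample size, power or target correlation for H1.C, so there is no figure to reproduce.

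**Inputs from the documents.** N = 40, two-sided 5%, correlation between assessments 0.45, and mood differences for HRSD 3.15±9, BDI 6.30±15, SIGH-SAD 7.0±11 and atypical score 4.45±5, with stated effect sizes .324, .378, .627 and .78 (all Section 9.2); 1:1 allocation (Section 6.2.2).

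**Assumptions.** The ± value is the SD of the paired difference. Correlation is exchangeable and there are 20 women per sequence. Mood and phase errors are independent, so there is no individual link. The documents give no phase effect, so it is varied.

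**Step 1: what the across-month slope measures.** With Months 2, 3 and 5 as times 0, 1 and 3, and y3 and y5 the changes from Month 2, the least-squares slope is (5·y5 − y3)/14. For responses of +1 h to AM and −0.5 h to PM:
- AM first: (5×(−0.5) − 1)/14 = −0.25 h/month.
- PM first: (5×1 + 0.5)/14 = +0.39 h/month.

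Identical responses give opposite signs. In general the sequences differ by 3/7 of the AM–PM difference (here 3/7 × 1.5 = 0.64).

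**Step 2: the correlation this creates.** Let m and p be the mood and phase treatment differences in SDs of their paired differences. The slope variance within a sequence is 3/28, and the sequences add (3/14)² times m² or p². Hence

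r = m·p / √[(m² + 7/3)(p² + 7/3)].

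For SIGH-SAD (m = .627) and p = 1: r = 0.627/√(2.726 × 3.333) = 0.21. The critical |r| for 40 women is 0.31. On Fisher's scale (SE 1/√37 = 0.164), the rejection rate is about 25%. Simulation gives 25.9%.

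**Step 3: simulated rejection rates with no individual link, stated effect sizes, 20,000 trials per cell.** One slope per woman over Months 2, 3 and 5:

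| Mood scale | p = 0.5 | p = 1 | p = 2 |
|---|---|---|---|
| HRSD | 6.7% | 11.2% | 17.9% |
| BDI | 7.6% | 13.0% | 23.0% |
| SIGH-SAD | 11.1% | 25.9% | 50.3% |
| Atypical | 14.2% | 35.8% | 67.1% |

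If either treatment effect is zero, the rate stays at about 5%.

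**Step 4: the same in hours.** Take mean/SD for HRSD, BDI and SIGH-SAD (0.35, 0.42, 0.636) and an assumed phase SD of 0.85 h. AM–PM differences of 0.5, 1.0 and 1.5 h are then p = 0.59, 1.18 and 1.76. Ranges run over the three scales:

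| Reading | 0.5 h | 1.0 h | 1.5 h |
|---|---|---|---|
| One slope per woman | 8–14% | 13–33% | 19–47% |
| 80 pooled changes | 9–14% | 13–29% | 17–45% |

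**Step 5: pooled changes with no phase effect.** A woman's two changes share a baseline and so correlate 0.5 in each measure. That multiplies the variance of r by about 1 + 0.5×0.5 = 1.25. The rate becomes P(|Z| > 1.96/√1.25 = 1.75) = 8%; simulation gives 7–8%.

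**Step 6: readings that remove treatment or sequence.** Over all cells of Step 3, sequence-adjusted slopes give 4.6–5.3%, within-woman AM–PM differences 4.7–5.3%, and the AM arm alone 4.8–5.2%.

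**Sensitivity.** Equally spaced visits (0, 1, 2) lower the SIGH-SAD row of Step 3 to 7.4%, 13.3% and 26.7%. If the mood slope also includes Months 4 and 6, with no effect assumed there, SIGH-SAD at p = 1 falls from 26% to 15% and HRSD from 11% to 7.5%.

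**The case against.** The best defence is that the plan is ambiguous, not committed to a faulty test. Section 9.1 words A and B as treatment contrasts from baseline to post-intervention, so C can be read as correlating those contrasts. The slopes in Section 9.6 are described within a random regression model with saturated treatment-by-time terms. If the individual slopes come from that model, treatment is already removed; taking out sequence-by-month means before computing slopes gives 4.6–5.2%. This part stands: the correlation cannot be said to be driven by sequence or treatment, only that it would be on two of the available readings. But the model text is attached to H1.A, and nothing carries its treatment terms into the correlation.

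A reader might also infer that H1.C would be confirmed whenever treatment moves both measures. The figures do not support that: in most cells the null is retained most of the time, and inflation is slight for HRSD with a small phase effect.

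Nor is linear regression in Section 9.1 against Pearson in Section 9.6 a conflict of substance; with one predictor the tests are identical. Neither, as written, carries an adjustment.

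Three further points count in part. The per-domain p-value correction would lower the absolute rates, though they would stay above the corrected threshold. Expectation is measured and examined against mood change, and the HRSD rater is blind; neither removes the treatment effect from the correlation. Finally, several analyses hold the nominal level, so the remedy below is not the only valid one.

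**Conclusion.** The point holds in conditional form. The slope for H1.C is undefined, and treatment and sequence are not accounted for. Taken across Months 2, 3 and 5, or as pooled changes, the Pearson test has type I error above 5%: from slight to roughly 47% over the Step 4 settings, and higher for the atypical score with a large phase effect. Inflation of the across-month slope requires non-zero treatment effects on both measures. H1.A and H1.B predict exactly that, so the test is least reliable in the situation the trial expects.

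The size rests on a phase effect and SD that the documents do not give, on reading ± as the SD of the paired difference, and on the mood visits included. The direction follows from the design.

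Severity: should-fix. The randomised mood comparison and its power are untouched; what is at risk is the mechanistic conclusion. Leaving the slope open also lets it be chosen after the data are seen.

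**What to change.** Replace the slope rule for H1.C. For each woman, compute the LWT+AM minus EWT+PM difference in post-treatment mood and the same difference in 6-SMT phase. The Month 2 baseline cancels: (AM − baseline) − (PM − baseline) = AM − PM. Regress the mood difference on the phase difference with sequence in the model, and test that coefficient. The sequence term also absorbs any period effect common to both measures. Name the mood scale and the 6-SMT timing measure in advance, and bring Sections 9.1 and 9.6 into line with this one method.

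The cost is SAP wording and one regression, with no new data. The downside is that only women with both periods contribute, against the plan's wish to use all available data. A within-arm correlation of changes from Month 2 can be listed as a supporting analysis to include women with one period. The plan should also state what the test can detect: with 40 women, 80% power needs a true correlation of about 0.43, before the small loss for the sequence term.
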